### 9.3.2. Follow-Up

Subjects will be followed from treatment start (or for comparator cohorts not defined by therapy: from an index date) until each outcome of interest, with death and emigration from Sweden treated as censoring events.

Some outcomes of interest in this study are thought to potentially occur at a higher rate while on drug, but that increased risk subsides after the drug is discontinued (ie, serious infections, herpes zoster, CV events, gastrointestinal (GI) perforation, progressive multifocal leukoencephalopathy (PML)). Those events will be evaluated over a risk window that includes time from drug initiation until 90 days after end of treatment. When a patient initiates a new therapy within the 90-day extension, the time and events during the overlapping period will be assigned to both treatments. The 90-day extension period is implemented in part to accommodate ongoing exposure to treatments with longer half-lives, and in part to ensure that any subclinical or undiagnosed illness at time of end of treatment is captured. As an additional sensitivity analysis for MACE, MI, serious infection, VTE, herpes zoster, PML, and gastrointestinal perforation events with a 90-day extension period applied after treatment discontinuation, if a new medication is started during the 90-day window after discontinuation of a previous medication, initiation of the new medication will stop the 90-day risk window, and any event prior to the new medication start will be assigned to the discontinued medication. Similarly, as part of the primary analysis, for malignancy and all-cause mortality events, a 90-day risk window will be applied to the censoring at switch approach (i.e., if a malignancy or death occurs in first 90 days after a patient has switched to a different therapy, follow-up time and the event will be attributed to prior therapy and not current therapy).

For non-melanoma skin cancer (NMSC), lung cancer, lymphoma and malignancies excluding NMSC, and all-cause mortality, the manifestation of which is expected to be delayed relative to the time of exposure, the outcomes will be evaluated using two different approaches, a once exposed always at risk approach as the primary analysis and a censor at switch approach as a secondary analysis. PML rates will also be described using this approach.

---

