**Appendix 4. ICD and MedDRA Codes For Select Safety Endpoints**

Event	ARTIS		BIOBADASER, BSRBR, RABBIT
	Operationalization	Validation ICD	Operationalization (Final list TBD based on reported endpoints).
Serious infections	Hospitalizations in the Patient Register listing as main diagnosis ICD10-codes below. If main diagnosis is RA, contributory diagnoses are also considered. A00-B99 (excluding A33 and A50), D73.3, E32.1, G00-G02, G04.2, G05-G07, H00.0, H44.0, H60.0-H60.3, H66-H67, H70, I30.1, I40.0, J00-J22, J32, J34.0, J36, J39.0-J39.1, J44.0, J85, J86, K04.4, K04.6, K04.7, K10.2, K11.3, K12.2, K14.0, K57.0, K57.2, K57.4, K57.8, K61, K63.0, K65.0, K65.1, K65.2, K65.9, L00-L08, L30.3, M00-M01, M46.2-M46.5, M60.0, M65.0, M71.0, M71.1, M72.6, M86, N13.6, N15.1, N15.9, N30.0 N30.8, N34.0, N41.2, N43.1, N45.2, N45.3, N45.4, N48.2, N61, N70, N73, N75.1	This algorithm has not been specifically validated in ARTIS, but the register itself is subject to strict quality assurance routines and has been validated several times. Refs: Ludvigsson et al. External Review and Validation of the Swedish National Inpatient Register, BMC Public Health, 2011 (11):450. http://www.socialstyrelsen.se/register/halsodataregister/patientregistret/inenglish .	Hospitalization and/or use of parenteral antibiotics+ MedDRA Infections and Infestations SOC 10021881.
HZ reactivation	Hospitalizations in the Patient Register listing as main diagnosis ICD10-codes B00 and B02. If main diagnosis is RA, contributory diagnoses are also considered.	The algorithm used to identify this endpoint in ARTIS has not been validated and is expected to only identify the most severe cases.	10019974 Herpes zoster, 10019983 Herpes zoster ophthalmic, 10030865 Ophthalmic herpes zoster, 10058428 Herpes zoster multi-dermatomal, 10063491 Herpes zoster oticus, 10065038 Herpes zoster disseminated, 10065119 Necrotising herpetic retinopathy, 10072210 Genital herpes zoster, 10074241 Varicella zoster gastritis, 10074245 Herpes zoster pharyngitis, 10074248 Herpes zoster meningoencephalitis, 10074253 Herpes zoster necrotising retinopathy, 10074254 Varicella zoster pneumonia, 10074254 Varicella zoster pneumonia, 10074259 Herpes zoster meningitis, 10074297 Herpes zoster cutaneous disseminated.

090177e199570500\Approved\Approved On: 13-Feb-2022 20:25 (GMT)

090177e199570500\Approved\Approved On: 13-Feb-2022 20:25 (GMT)

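### The Appendix 4 serious-infection list lacks N10, N12, N39.0, I33 and T84.5, so some hospitalised infections are not counted and absolute rates are biased low

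*Protocol*

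**What the plan says.** Appendix 4, serious-infections row, ARTIS column, sets the ascertainment rule: "Hospitalizations in the Patient Register listing as main diagnosis ICD10-codes below. If main diagnosis is RA, contributory diagnoses are also considered". A fixed list of ICD-10 codes follows. Its circulatory part is the two codes in the run "H66-H67, H70, I30.1, I40.0, J00-J22". The genitourinary part begins in the run "M65.0, M71.0, M71.1, M72.6, M86, N13.6, N15.1, N15.9, N30.0 N30.8, N34.0" and, in full to the end of the list, reads "N13.6, N15.1, N15.9, N30.0 N30.8, N34.0, N41.2, N43.1, N45.2, N45.3, N45.4, N48.2, N61, N70, N73, N75.1".

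For the other European registers, the same row uses a different definition: "Hospitalization and/or use of parenteral antibiotics+ MedDRA Infections and Infestations SOC 10021881".

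Section 9.3.3 lists the endpoint as hospitalised infections overall. Section 9.7.2 says ARTIS will apply an ICD-based algorithm to identify serious infections in the Patient Register and points to Appendix 4 for it. A later paragraph of Section 9.7.2 says the final SAP will also specify an ICD algorithm harmonised with the other registers. Sections 8 and 9.1 make the estimation of event rates the main task. Comparison by hazard ratio depends on feasibility.

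**The concern.** A closed list defines the endpoint completely: an infection whose code is not on it cannot become an event, however severe the admission. This list includes narrow entities such as N15.1, N34.0 and N48.2, and infective pericarditis and myocarditis (I30.1, I40.0). It passes over neighbouring codes for pyelonephritis, urinary infection of unspecified site and endocarditis, and it stops before the T chapter, where joint-prosthesis infection is coded. Joint replacement is common enough in this population to be tracked as a baseline history item in Appendix 2.

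The printed algorithm is therefore narrower than the endpoint named in Section 9.3.3. Serious infection is an important identified risk in Section 7.1, and its rate is one of the figures the study exists to report. The row does not say that whole groups of infections are left out. The herpes zoster row below it does warn that only the most severe cases will be found.

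**Working it through.** **Inputs.** The code list and the main-diagnosis rule come from Appendix 4, and the endpoint name from Section 9.3.3. The code labels are the standard ICD-10 ones. The Protocol adopts ICD-10 in Section 9.4.3 but does not print the labels, so they are the one input from outside the document.

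**Step 1: is each code on the list?** All ranges were expanded. The list runs in code order, so a missing code shows as a gap.

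| Code | Standard label | Listed codes on either side | Listed? |
|---|---|---|---|
| N10 | acute pyelonephritis | M86, then N13.6 | no |
| N12 | pyelonephritis not stated as acute or chronic | M86, then N13.6 | no |
| N39.0 | urinary tract infection, site not specified | N34.0, then N41.2 | no |
| I33 | acute and subacute endocarditis | I30.1, then I40.0 | no |
| T84.5 | infection of a joint prosthesis | list ends at N75.1 | no |

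The separator between N30.0 and N30.8 is missing in the text. Reading it as a comma or as a range changes none of these results.

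**Step 2: what is captured nearby?** N13.6, N15.1, N15.9, N30.0 and N30.8 are listed, so part of urinary infection counts. The A00-B99 block takes in sepsis (for example A41.9) and some organism-coded endocarditis (for example B37.6). M00-M01 takes in M00.9, and J00-J22 takes in J18.9. The omission is of specific codes, not of whole organ systems.

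**Step 3: does the main-diagnosis rule recover the missing admissions?** Contributory diagnoses are read only when RA is the main diagnosis, and then against the same list. With N10 as main diagnosis, a listed code in a secondary position does not make the admission an event. With RA as main diagnosis and T84.5 as the contributory code, there is no event either.

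**Step 4: effect on the estimates.** Let m be the share of first hospitalised infections that the list misses. To a first approximation:

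- observed rate = true rate × (1 − m)
- observed hazard ratio = true hazard ratio × (1 − m for tofacitinib) / (1 − m for the comparator)

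The rate is too low whenever m is above zero. A patient with a later listed admission is still counted, but late. The hazard ratio moves only if m differs between cohorts. The documents give no value of m, overall or by cohort, so neither expression can be evaluated. The planning rate of 30/1000 PY in Section 9.5 does not help: it is attributed to earlier register analyses held by the sponsor, and nothing says which code list produced it.

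**The case against.** The strongest reply is that the list is not final. Section 9.7.2 promises a harmonised algorithm in the SAP. Appendix 2 says outcome details will be agreed before each comparative report. Section 9.3.3 allows sub-diagnoses to be added before the feasibility analysis and the final report. This stands to the extent that the SAP may replace the list. But the harmonisation sentence sits in the paragraph on adjusted comparative reports. Nothing there says which codes are missing, and the Protocol prints no other ICD list for the descriptive rates.

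A second reply is that the algorithm is a disclosed choice. Section 9.7.2 and Appendix 4 say it has not been validated, and Section 9.7.2 justifies it by the need to set results beside historical findings. That is a good reason to keep reporting the current list. It does not make the list match an endpoint named as hospitalised infections overall. The register's positive predictive values of 85% to 95% do not bear on the gap either, because they describe recorded diagnoses that prove correct, not infections the list never looks for.

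A third reply is that equal under-capture in all cohorts leaves the hazard ratio alone. That is correct, but the hazard ratio is the conditional, secondary output. The rates are low regardless.

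On pooling, the contrast with the other registers is real, but their column is headed as not yet final. Section 9.7.2 already makes pooling conditional on a heterogeneity evaluation. Their definition also admits parenteral antibiotic use without admission, so adding five codes would narrow the difference without removing it.

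**Conclusion.** The point holds for the code list. Admissions with N10, N12, N39.0, I33 or T84.5 as main diagnosis are not counted, and absolute serious-infection rates are biased low in every cohort where such admissions occur. The size cannot be computed from the documents. The conclusion rests on the standard ICD-10 labels and on the printed list being the one applied, as Section 9.7.2 states.

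A reader might infer more, and the documents do not support it:

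- **Fatal infections outside hospital.** Section 9.3.2 follows patients "with death and emigration from Sweden treated as censoring events", and MACE in Appendix 4 does use cause of death. But the endpoint is hospitalised infection, so a death without admission lies outside it and is not an under-count. All-cause mortality is a separate endpoint.
- **Urinary infection and endocarditis wholly missed.** They are missed only in part, as Step 2 of the working shows.
- **Serious infection as the lead endpoint.** It is first in the title, but no endpoint is so designated, and Section 9.3.1 calls VTE primary.
- **A shortfall that favours tofacitinib.** This needs a larger missed share in tofacitinib patients, and no document gives one. For joint-prosthesis infection, joint replacement is an adjustment term in models HRb and HRc of Appendix 2, which would at least partly reduce such an imbalance.
- **A stated percentage loss.** Any figure would be assumed.

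**What to change.** In the serious-infections row of Appendix 4, add N10, N12, N39.0, I33 and T84.5 to the ARTIS list. Carry the same list into the harmonised SAP algorithm promised in Section 9.7.2, so that descriptive and comparative results use one definition. Also report rates with the current list, to keep the comparison with earlier ARTIS results that Section 9.7.2 values. The difference between the two rates would show how much these codes matter.

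The cost is small: a changed code list and one extra outcome run on data already linked. The main rate would no longer be directly comparable with historical ARTIS rates, and the retained current-list rate covers that.

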### **7.1. Serious Infections**

The risk of infections among RA patients depends on the environmental distribution of the organism of interest, inherent patient characteristics and treatment for RA. Persons with RA  $\geq 65$  years of age are found to be at increased risk of serious infections relative to those  $< 65$  years of age in both clinical trial and observational data. The mechanism by which infection risk is increased in RA patients is likely to be multifactorial. In addition to the underlying disease (RA), therapies used to treat the disease have suppressive effects on the immune system. For example, TNFi may affect host defense against infection since TNF mediates inflammation and modulates cellular immune response. Tofacitinib inhibits cytokines that are integral to lymphocyte activation, proliferation, and function, and inhibition of their signaling may thus result in modulation of multiple aspects of the immune response.

Risk of infections is reportedly higher among TNFi-treated patients than those on DMARDs, however studies looking at TNFi-treated cohorts over time have shown that rates of serious infection decline over time. The decline may reflect a change in the risk profile of the population as a result of at-risk patients switching therapies, reduced co-administration of corticosteroids, in addition to any impact of TNFi therapy on overall health.

Tuberculosis (TB) is the most common opportunistic infection (OI) in the RA population, with risks approximating 10-20 times that of the general population, likely due in part to RA therapy.

Studies comparing the background risk of herpes zoster in RA and general population cohorts have been inconsistent, with some showing no increased risk and some showing modestly elevated risk.

Serious infections, including tuberculosis and herpes zoster are important identified risks for RA patients taking tofacitinib.

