### 9.3.3. Endpoints of Interest

The endpoints of interest captured in the semi-annual reports are the following safety events of interest.

For the interim feasibility analysis and final safety report (where also information on patients, co-variates and outcomes, from SRQ as well as from the linked Patient/Prescribed Drug and other registers will be included) of pre-specified safety outcomes, the following events of interest have been pre-specified.

1. Hospitalized infections overall.
2. Opportunistic infections.
3. Herpes zoster (hospitalized).

090177e199570500\Approved\Approved On: 13-Feb-2022 20:25 (GMT)

4. Hepatitis.
5. Fractures.
6. NMSC.
7. Malignancies (overall, excluding NMSC).
8. Lung Cancer.
9. Lymphoma (overall and independently by subtype, including non-Hodgkin lymphoma, Hodgkin lymphoma, and chronic lymphatic leukemia).
10. CV events, including deep vein thrombosis/pulmonary embolism (DVT/PE).
11. Major Adverse Cardiovascular Events (MACE).
12. Myocardial infarction (MI)
13. Gastrointestinal (GI) perforations.
14. Progressive multifocal leukoencephalopathy (PML).
15. Interstitial lung disease, pending feasibility.
16. All-cause Mortality.

Given the age-dependent rate events of interest, analysis will be conducted in elderly patents aged  $\geq 65$  years.

This list may be extended with a reasonable number of additional sub-diagnoses or new health related outcomes as agreed to by ARTIS researchers and Sponsor before the interim feasibility analysis and final safety report. These decisions will be made prior to initiation of analyses and documented in a statistical analysis plan (SAP) kept on file by the Sponsor.

In addition, the final safety reports will include the number of tofacitinib-exposed pregnancies.

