For these analyses, the exposure cohorts will be analyzed overall, by previous biologics use and monotherapy and combination therapy with concomitant conventional synthetic disease modifying antirheumatic drugs (csDMARDs). Increased risk of malignancy (excluding NMSC), MACE, MI, serious infection, VTE, herpes zoster, PML, and gastrointestinal perforation events, as well as an increase in mortality, in patients treated with a combination therapy with MTX specifically will be described if sample sizes are sufficient, in the interim and final reports. These and potentially other agreed upon strata will be determined a priori and included in SAP filed with Sponsor. The general analytic approach will be descriptive and include rates of events of interest within stratified treatment cohorts. Data will be presented as number of events, crude and age/sex-standardized incidence rates.

Any final comparative report will adjust for differences in severity of disease and other confounders will be completed using appropriate multivariate, propensity score matching, or inverse probability weighting. The final report will also evaluate the rates of safety events of interest within the elderly. The outcomes reported will include hospitalized infections, OI, herpes zoster, fractures, hepatitis, GI perforations, malignancies, CV events, and all-cause mortality, with subgroupings and selected additional outcomes per agreement. HRs from multivariable Cox regressions adjusting for sex, age, year of treatment start, treatment history, disease severity, comorbidities, and other potential confounders to be agreed upon by ARTIS and the Sponsor and defined in an SAP prior to analysis. The final SAP will also specify an ICD-algorithm harmonised with other registers conducting similar analyses for serious infections, CV events, GI perforations, and herpes zoster (HZ).

Any comparative safety reports will leverage data linkages to obtain data on all comorbidities that have led to hospitalization, cancer or death. Data on malformations and perinatal morbidities and mortality can also be obtained from the birth register.

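### The ARTIS code list for hospitalised herpes zoster includes B00 (herpes simplex), so simplex admissions are counted as zoster and the zoster rate is overstated in every cohort

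*Protocol*

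**What the plan says.** Section 9.3.3 lists the endpoint as "Herpes zoster (hospitalized" and names no other herpesvirus infection. Section 7.1 explains its standing: "Serious infections, including tuberculosis and herpes zoster are important identified risks for RA patients taking tofacitinib". Section 9.3.2 gives it the on-drug plus 90-day risk window and a sensitivity analysis of that window. Section 9.7.2 adds a description of patients on combination therapy with methotrexate.

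The operational definition is in the Appendix 4 row labelled HZ reactivation. For ARTIS it reads "Hospitalizations in the Patient Register listing as main diagnosis ICD10-codes B00 and B02"; contributory diagnoses are considered when the main diagnosis is RA. The validation cell of that row says: "The algorithm used to identify this endpoint in ARTIS has not been validated and is expected to only identify the most severe cases". The cell for the other European registers begins "10019974 Herpes zoster, 10019983 Herpes zoster ophthalmic" and continues with further zoster and varicella-zoster terms.

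Section 9.4.3 names ICD-10 as the Patient Register's coding system since 1997. Section 9.7.2 says that Appendix 4 describes the algorithms ARTIS uses, and also looks ahead: "The final SAP will also specify an ICD-algorithm harmonised with other registers conducting similar analyses", with herpes zoster among the endpoints named.

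**The concern.** The label and the code list do not describe the same disease. B02 is zoster. B00 is the separate category for herpes simplex infection. These meanings are standard ICD-10; the protocol does not spell them out. An admission correctly coded B00 would enter the numerator of an endpoint named herpes zoster.

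The main product of the study is descriptive: event rates with 95% confidence intervals in four cohorts. The error therefore reaches the primary objective directly, without any comparative model. It would also pass into any hazard ratio estimated later, and into what ARTIS contributes to the meta-analytic summary planned in Section 9.7.2.

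**Working it through.** **Is there a figure to reproduce?** No. Section 9.5 gives power for assumed rates of 30, 10 and 6 per 1000 person-years, exemplified by serious infection, malignancy and MACE. The protocol states no zoster rate, event count or power, so no printed number depends on this code list.

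**Side-by-side check of the definition.**

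- Endpoint named in Section 9.3.3: hospitalised herpes zoster.
- ARTIS codes in Appendix 4: B00 and B02.
- Other registers, same row: zoster and varicella-zoster terms, plus one term not specific to zoster (necrotising herpetic retinopathy). There is no herpes simplex term.
- Stated caveat: the algorithm is unvalidated and finds only the most severe cases. That concerns missed zoster (sensitivity). It does not disclose that another infection is counted (specificity).
- Register accuracy in Section 9.7.2: inpatient positive predictive values generally of 85% to 95%. These concern whether the recorded diagnosis is right, not whether the right code was chosen.
- Where B00 is already counted: the serious infections row, whose range starts "A00-B99 (excluding A33 and A50), D73.3, E32.1".

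No passage gives a reason for B00.

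**Size, under assumption.** Let s be the share of a cohort's counted events that are B00. The documents do not give s; 10% to 50% is assumed here to show a range. The two event types are treated as additive, which is close when few patients have both.

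Rate overstatement in a cohort with share s = 1/(1 − s).

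For the hazard ratio, let s be the share among comparator events, HRz the hazard ratio for zoster and HR0 the hazard ratio for simplex:

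Observed HR = (1 − s) × HRz + s × HR0.

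| s | Rate overstated by | HRz 2.0, HR0 1.0 | HRz 1.5, HR0 1.0 | HRz 2.0, HR0 2.0 |
|---|---|---|---|---|
| 10% | 1/0.9 = 1.11 | 1.9 | 1.45 | 2.0 |
| 20% | 1/0.8 = 1.25 | 1.8 | 1.40 | 2.0 |
| 30% | 1/0.7 = 1.43 | 1.7 | 1.35 | 2.0 |
| 50% | 1/0.5 = 2.0 | 1.5 | 1.25 | 2.0 |

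The direction for the ratio depends wholly on HR0. If HR0 were 3.0 with HRz 2.0 and s 30%, the observed value would be 0.7 × 2.0 + 0.3 × 3.0 = 2.3, which is above the zoster hazard ratio. The rate, by contrast, is overstated in any cohort that has simplex admissions, whatever HR0 is.

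**The case against.** The strongest reply is that the protocol leaves the operative definition open. Section 9.7.2 promises a harmonised ICD algorithm for herpes zoster in the SAP, Section 9.7 lets the SAP modify the plan, and Appendix 2 says that outcome definitions will be agreed before each report. The SAP is not at hand and may already use B02 alone. This stands in part: the plan has a step at which the error could be caught. But Section 9.7.2 presents Appendix 4 as the algorithms ARTIS uses, and the row states a code list instead of leaving a blank. It is a wrong stated rule, not missing detail.

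Three further objections stand and limit the point.

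- A reader might infer that B00 dilutes the tofacitinib signal for zoster. The documents do not support that. Dilution needs a smaller tofacitinib effect on simplex than on zoster, and no passage says so; Section 7.1 describes modulation of several aspects of the immune response. A hazard ratio may also never be estimated, since comparison is pending feasibility.
- A reader might infer that dropping B00 would make ARTIS comparable with the other registers. It would not by itself. Their cell carries no hospitalisation condition, whereas ARTIS counts admissions only, and their list includes the non-specific retinopathy term. Section 9.7.2 expects heterogeneity even with harmonised coding.
- A reader might extend the error to the baseline variable for history of herpes zoster. Section 9.3.1 gives no codes for it, so no error is shown there.

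**Conclusion.** The point holds for the endpoint definition. As Appendix 4 stands, simplex admissions count as hospitalised zoster, and the descriptive rate of a named identified risk is overstated in every cohort. The overstatement is 1.11 to 2.0 times if simplex is 10% to 50% of counted events; that share is an assumption, and a small share would make the effect small. Any hazard ratio would describe a mixture of two infections. Whether it lies below, at or above the zoster hazard ratio cannot be said from the documents. The conclusion rests on the standard meaning of the two ICD-10 categories and on Appendix 4 being applied as printed.

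**What to change.** Restrict the ARTIS cell of the HZ reactivation row in Appendix 4 to B02, and write the same restriction into the harmonised algorithm that Section 9.7.2 assigns to the SAP, before the feasibility assessment and the final report are run. If simplex is of interest, report B00 as a separately named outcome. If B00 was included on purpose, rename the endpoint, give the reason and show the two codes separately.

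No safety event is lost, because B00 remains within the serious infections range. The cost is one code in the appendix and in the extraction program, and fewer counted events. The standard error of a log rate is about 1/√(events), so it rises by 1/√(1 − s): 1.05 times at an assumed share of 10% and 1.41 times at 50%. With fewer events, a comparison could also miss the minimum of 5 per cohort set in the Appendix 2 table notes. The precision given up belonged to a different endpoint.
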